**Table 7-1: Overview of Additional Objectives**

[figure not shown]
End Point of Additional Objective	Scale/Data Collection	Baseline	1-Month	3-Month	6-Month	12-Month
1. Change from baseline in overall pain intensity A	VAS	✗	✓	A	✓	✓

[figure not shown]
A. Primary Objective is to characterize change from baseline to 3-months.

[figure not shown]
### 7.9.3.1 Change in overall pain (VAS)

[figure not shown]
Changes in overall pain intensity, as measured by VAS, from Baseline to 1-, 6-, and 12-Month visit will be analyzed for both the Per-protocol Analysis Set and the Completers Analysis Set. Change in overall pain intensity will be calculated using VAS at the 1-, 6-, and 12-Month visit minus VAS at the baseline visit. A negative change is an improvement. The 95% CI of the mean change will be calculated. Scores at all visits will be summarized.

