Statistics	
The Confidence Intervals for One Mean module in statistical software PASS 11 was used to provide the following sample size justification: a sample size of 30 subjects produces a two-sided 95% confidence interval with a distance from the mean to the limits that is equal to 0.97 when the estimated standard deviation is 2.6.
 
With estimated attrition of 40% between enrollment and implant and 10% between implant and 3-Month, to achieve approximately 30 subjects at 3-Month visit, up to 56 subjects may be enrolled into the study.
 
For the primary objective, the mean change of overall pain intensity from baseline to 3-Month visit will be reported with a 95% confidence interval (CI). Primary analysis will use per-protocol analysis set who are implanted, follow DTM-LE SCS programming, and provide data at both baseline and 3-Month visits. Sensitivity analyses will use completers analysis set who are implanted and provide data at both baseline and 3-Month visits regardless of

	
programming patterns, as well as implanted analysis set with multiple imputation (MI) for missing data.
 
The secondary objective will be analyzed with descriptive statistics from Device Trial to 12-Month visit. Subjects who contribute to follow-up visits will be included in the analysis.
 
[REDACTED]
 
Adverse events and device deficiencies will be summarized using summary tables displaying the frequency and percentages. Adverse events will be summarized by seriousness as well.

--	---

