### **10.12.3 6-Month Visit**

The 6-Month visit will occur 180 days  $\pm$  30 days after device activation (Day 0). If there is not a  $\geq$  50% decrease in the VAS for overall pain collected at the visit compared to the Baseline VAS for overall pain, the subject may be re-programmed. If re-programming occurs, device interrogation report(s) with initial and final programmed settings will be uploaded via CDU. Imaging may be performed to assess for lead migration if deemed necessary by the investigator.

The following information will be collected during the 6-Month Follow-up visit:

[figure not shown]
- VAS
- Programming parameters/device interrogation report(s) with initial and final settings
- Imaging (if performed)
- Changes to pain medications
- AEs/DDs

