## 7.4 Handling of Missing, Unused, and Spurious Data and Dropouts

Missing data are a potential source of bias when analyzing study data. A rigorous study design and execution will help prevent the incidence of missing data from occurring.

The primary analysis of the primary and secondary objectives will include subjects who follow DTM-LE programming and provide data (Per-protocol Analysis Set). Sensitivity analyses will be performed for the primary objective using Completer Analysis Set, as well as Implanted Analysis Set with the Multiple Imputation (MI) methodology for missing data.

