### **7.9.1.4 Determination of Subjects/Data for Analysis, Sensitivity Analysis**

The primary analysis will use subjects who are implanted with Intellis neurostimulator, follow DTM-LE programming, and provide outcome measures at both baseline and 3-Month visit (Per-protocol Analysis Set).

Two sensitivity analyses will be performed. The first uses the Completers Analysis Set (7.1.3) who have outcome measures at both baseline and 3-Month visit and will be performed in the same way as the primary analysis method above. The other sensitivity analysis uses the Implanted Analysis Set (7.1.3) and will be performed using Multiple Imputation (MI) method for missing data at the 3-Month Visit. For scheduled 3-Month visit, if an Unscheduled Visit occurred within the 3-Month visit window, and the VAS is collected at the Unscheduled Visit, the VAS from the Unscheduled Visit will be used in the analysis of the 3-Month visit. Otherwise, the missing VAS will be imputed using MI. Prior to the use of MI, the distributions of the continuous variables will be assessed for normality and transformation may be considered if they are not normally distributed. The model variables in MI may include, but are not limited to study site, subject age, gender, primary diagnosis, VAS at baseline, 1-Month visit. The fully conditional specification method with 10 burn-in iterations within SAS and 10 repetitions (M = 10) will be used for imputation. Constraints will be set so that the imputed VAS are restricted to values ranging from 0-10. Following imputation, the objective will be evaluated using MI analysis method.

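### Change in overall VAS at 1, 6 and 12 months is estimated only from subjects with data at the visit; the all-implanted imputation analysis stops at 3 months, so durable relief may be overstated if subjects exit for lack of effect

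*SAP*

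**What the plan says.** For overall VAS at 1, 6 and 12 months, SAP 7.9.3.1 states that the change from baseline "will be analyzed for both the Per-protocol Analysis Set and the Completers Analysis Set". A 95% CI of the mean change is to be given. No other set and no imputation is named for those visits.

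The Protocol Synopsis (Statistics) describes the two sets. Per-protocol subjects are those "who are implanted, follow DTM-LE SCS programming, and provide data at both baseline and 3-Month visits". The other is the "completers analysis set who are implanted and provide data at both baseline and 3-Month visits regardless of" programming pattern. Both descriptions are tied to the 3-Month visit. SAP 7.9.2.4, on the secondary objective, shows the SAP applying the same sets by available data at each visit.

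At 3 months there is a further layer. SAP 7.9.1.4 says that the Implanted Analysis Set analysis "will be performed using Multiple Imputation (MI) method for missing data at the 3-Month Visit", and Protocol 14.4.4 agrees. SAP 7.4 fixes the scope: "Sensitivity analyses will be performed for the primary objective using Completer Analysis Set, as well as Implanted Analysis Set with the Multiple Imputation (MI) methodology".

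**The concern.** A mean change at 12 months will be read as evidence on whether relief lasts. All implanted subjects with activated devices are meant to be followed to that visit (Protocol 6), so the natural denominator is everyone implanted. The planned estimate leaves out any implanted subject without a 12-month VAS. In Per-protocol it also leaves out subjects no longer on DTM-LE programming.

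The documents give reasons to think that absence may depend on outcome. Protocol 11.2 names too little relief as an example of why a subject may withdraw. Protocol 10.21 foresees discontinuation for lack of effectiveness and ends data collection at exit, so those later scores are missing for good. Protocol 10.16 lists ineffective or lost therapy among the reasons for revision or explant, with continuation in the study decided case by case.

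The plan itself calls missing data a potential source of bias (Protocol 14.1.2 and 14.9, SAP 7.4). It answers this with an all-implanted analysis at 3 months but offers only prevention afterwards, although exits can only accumulate.

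**Working it through.** **1. The plan's own figures.** The Protocol Synopsis states that "a sample size of 30 subjects produces a two-sided 95% confidence interval" with half-width 0.97 at SD 2.6.
- Half-width = t(0.975, n-1) x SD/sqrt(n) = 2.045 x 2.6/sqrt(30) = 0.971. This reproduces 0.97.
- Enrollment = 30/(0.60 x 0.90) = 55.6, rounded up to 56. This also reproduces.
- Implied implanted set = 56 x 0.60 = 33.6, about 34. Expected at 3 months = 33.6 x 0.90 = 30.2.

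No stated number is in dispute.

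**2. Who is counted at each visit.**

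| Implanted subject | Per-protocol | Completers | Implanted with MI |
|---|---|---|---|
| VAS recorded, on DTM-LE | counted | counted | 3 months only |
| VAS recorded, off DTM-LE | not counted | counted | 3 months only |
| No VAS at the visit | not counted | not counted | 3 months only |

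The last row is the gap: at 1, 6 and 12 months no analysis includes those subjects.

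**3. How a subject leaves a set.** At 3 and 6 months, if overall VAS has not fallen by at least 50% "compared to the Baseline VAS for overall pain, the subject may be re-programmed" (Protocol 10.12.2 and 10.12.3). Reprogramming is not exit. It never removes a subject from Completers, and it removes one from Per-protocol only if the new settings fall outside DTM-LE limits, which SAP 7.10 anticipates. Leaving Completers requires a missing VAS, through exit or a missed assessment.

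**4. Size of the shift.** Let p be the share of implanted subjects left out and d the difference in mean change between those left out and those kept. The mean of those kept differs from the all-implanted mean by p x d. The documents give 10% attrition from implant to 3 months and nothing for 3 to 12 months, so both p and d are assumptions.
- Working range: 0.10 x 2 = 0.2 cm; 0.30 x 3 = 0.9 cm.
- Wider range: 0.10 x 1 = 0.1 cm; 0.40 x 4 = 1.6 cm.

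Against 0.97, the working range runs from about one fifth of the half-width (0.2/0.97 = 0.21) to nearly all of it (0.9/0.97 = 0.93). The share p differs between the sets and cannot be larger for Completers than for Per-protocol.

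**5. Precision at 12 months, SD 2.6.** If 10, 20, 30 or 40% of 34 are left out, n is about 31, 27, 24 or 20, and the half-width is 0.95, 1.03, 1.10 or 1.22. With all 34 observed it would be 0.91. An MI interval would be wider than that, because imputation adds variance. None of these intervals reflects the shift in step 4.

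**The case against.** A reader might infer that long-term relief is estimated only from subjects who did well, or that the 12-month mean is conditional on success. The documents do not support that. Neither visible definition selects on pain score. A subject with poor relief, or one moved off DTM-LE, stays in Completers as long as a VAS is recorded. After a system modification the visit schedule is unchanged (Protocol 10.16). Exit may also follow pregnancy, relocation, loss to follow-up or adverse events (Protocol 10.21), and nothing says which reason will dominate. This part of the objection stands, and the direction of bias must be worded as possible only.

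Second, the plan is not blind to the problem. The contrast between Per-protocol and Completers shows the effect of dropping off-programming subjects. Disposition is tabulated by visit to 12 months (SAP 7.1.1), and an exit reason is recorded for every subject (Protocol 10.21). Out-of-window visits are used (Protocol 10.3), and conditional disengagement lets some data still be collected (Protocol 10.21.3). This narrows the gap to subjects with no VAS at the visit but does not close it: counts and reasons do not show how far the mean would move.

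Third, SAP 7.1.3, which defines the sets, is not legible in the public version. How they are applied at 6 and 12 months is therefore inferred. Even so, SAP 7.9.3.1 names its two sets, and Implanted is not one of them.

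Fourth, MI and repeated-measures models ordinarily assume missing at random. If relief is lost after the last recorded VAS and the subject then leaves, neither removes the bias. That limits what the remedy can show. It is a reason to state the assumption, not to omit the analysis.

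**Conclusion.** The point holds in a limited form. At 1, 6 and 12 months the mean change in overall VAS rests only on subjects with data at the visit and, in Per-protocol, only on those still on DTM-LE programming. If subjects exit for lack of effect, which the protocol foresees, durable relief may be overstated, and no visible analysis examines this. The all-implanted analysis that would do so exists for 3 months only.

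The magnitude is not determinable from the documents. The 0.2-0.9 cm range depends wholly on the assumed 10-30% absent and 2-3 cm gap. Only its upper end approaches the 0.97 planning half-width, and if absence is unrelated to outcome there is no shift. The objective is additional and descriptive, without a hypothesis test, and the primary 3-month endpoint is unaffected. This is a low-cost improvement that is worth making, not a flaw in the main result.

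**What to change.** Add to SAP 7.9.3.1 a supportive analysis of change in overall VAS at 1, 6 and 12 months in the Implanted Analysis Set, regardless of programming, by one of two routes:
- extend the MI of SAP 7.9.1.4 to these visits, with earlier VAS values as predictors; or
- fit a likelihood-based repeated-measures model of VAS change at 1, 3, 6 and 12 months, with baseline VAS as covariate.

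At 1 month the only earlier VAS is baseline, so imputation there has little to draw on; the repeated-measures model uses all visits together.

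Report beside the estimates the number of implanted subjects missing at each visit and the reasons, and state that the analysis assumes missing at random.

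The cost is a few lines of SAP text and modest programming. It uses VAS scores already scheduled for collection and needs no new visits or subjects. The sponsor accepts that the long-term estimate may look less favourable.

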## 7.10 Safety Evaluation

All device-related, therapy-related, and procedure-related adverse events and device deficiencies from the Device Trial Start Visit until study exit will be characterized.

Adverse events and device deficiencies will be coded and summarized using the most recent version of Medical Dictionary for Regulatory Affairs (MedDRA).

The adverse events will also be categorized by relationship to study device and/or therapy. Adverse events will be presented in summary tables displaying the number of serious events, the number of events, and the number and percentage of subjects with one or more events. A summary of all device or therapy related adverse events and of any deaths will also be provided. A narrative of each serious device- or therapy-related adverse event will be provided.

Device deficiencies will be presented in summary tables displaying the number of deficiencies, and the number and percentage of subjects with deficiencies.

Device exposure will be summarized by analysis set and is considered from the time the subject is first exposed to the neurostimulation system (at the beginning of the device trial) until the product is explanted, or the subject discontinues from or completes the study, if later. Amount of exposure will be summarized (in months) using descriptive statistics such as mean, standard deviation, minimum, and maximum.

Data from the Scheduled Follow Up CRF will be evaluated for subjects in the Completer Analysis Set to determine whether subjects were programmed within DTM-LE limits during the study. For subjects who

were programmed within DTM-LE limits, the months of DTM-LE exposure will be computed in the same way as above, with the Cut-off Date for DTM-LE extending until the date at which it was reprogrammed out of DTM-LE limits.

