Device Related  (includes all implantable components and features, associated introduction tools, operational and installed software and programmers as defined in the CIP, see Section 7.1 )	An AE that results from the presence or performance of any component of the system.  Neurostimulator-related : An AE that results from the presence or performance (intended or otherwise) of the neurostimulator. Lead-related : An AE that results from the presence or performance (intended or otherwise) of the lead. Extension-related : An AE that results from the presence or performance (intended or otherwise) of the extension. External Study Device-related : An AE that results from the presence or performance (intended or otherwise) of an external study device (e.g., programmer, ENS).
Therapy Related	Event related to therapy delivery by device. Normally therapy-related events resolve when the device is turned off or reprogrammed. This category should not include events that resulted from a malfunction of the device (i.e. hardware-related events).
Procedure Related	An AE that occurs due to any procedure related to the implantation or surgical modification of the system.

Seriousness	
Serious Adverse Event (SAE)	
AE that led to any of the following
 
a) death, b) serious deterioration in the health of the subject, users or other persons as defined by one or more of the following: 1) a life-threatening illness or injury, or 2) a permanent impairment of a body structure or a body function, including chronic disease, or 3) in-patient or prolonged hospitalization, or 4) medical or surgical intervention to prevent life-threatening illness or injury or permanent impairment to a body structure or a body function, c) fetal distress, fetal death or a congenital abnormality or birth defect including physical or mental impairment
 
NOTE 1: Planned hospitalization for a pre-existing condition, or a procedure required by the CIP, without serious deterioration in health, is not considered an SAE. (ISO 14155:2020, 3.45)

Serious Adverse Device Effect (SADE)	Adverse device effect that has resulted in any of the consequences characteristic of a serious adverse event. (ISO 14155:2020, 3.44)

Causality	

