**14.7 Safety assessment**

To characterize all device-related, therapy-related, and procedure-related adverse events and device deficiencies from the Device Trial Start Visit until study exit. Adverse events and device deficiencies will be summarized using summary tables displaying the frequency and percentages. Adverse events will be summarized by seriousness as well.

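### SAP 7.10 promises to characterise procedure-related adverse events, then omits procedure from the relatedness categories, the related-event summary and the serious-event narratives

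*SAP*

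**What the plan says.** SAP 7.10 begins with a scope of three classes: "All device-related, therapy-related, and procedure-related adverse events and device deficiencies from the Device Trial Start Visit until study exit will be characterized". Protocol 14.7 sets the same scope: "To characterize all device-related, therapy-related, and procedure-related adverse events and device deficiencies from the Device Trial Start Visit until study exit". Protocol Table 12-1 defines procedure-related as a class of its own, "An AE that occurs due to any procedure related to the implantation or surgical modification of the system", and Table 12-2 assigns the relatedness classification, with procedure as one of the three parameters, to both investigator and sponsor.

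Three later sentences of SAP 7.10 say how relatedness will be reported:

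- Categorisation: "The adverse events will also be categorized by relationship to study device and/or therapy".
- Related-event summary: "A summary of all device or therapy related adverse events and of any deaths will also be provided".
- Narratives: "A narrative of each serious device- or therapy-related adverse event will be provided".

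Two other outputs in the same section carry no restriction by relatedness. One is the coding and summary of events: "Adverse events and device deficiencies will be coded and summarized using the most recent version of Medical Dictionary for Regulatory Affairs (MedDRA"). The other is the set of general tables: "Adverse events will be presented in summary tables displaying the number of serious events", together with counts of events and of subjects affected.

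**The concern.** The section states an aim covering three classes and then specifies relatedness outputs for two. The class left out is the one that covers surgical harm. Protocol 11.1.1.1 lists spinal fluid leak, bleeding, infection and paralysis among the risks of implanting the system, and each implanted subject goes through a trial lead placement (10.8.1) and a permanent implant (10.9).

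SAP section 3 describes the plan as covering all the analyses in the final report, so a procedure-related table or narrative that is not written down cannot be assumed. Protocol section 13 provides for no clinical events committee, adverse events advisory committee or data monitoring committee. Ongoing review is by sponsor personnel, including the Medical Advisor. The SAP's tables and narratives are therefore the main planned written account of safety, and a reader of the final report could not tell from them which events were attributed to surgery.

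**Working it through.** No sample size, rate or precision figure is involved, so the check is a comparison of texts.

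**Step 1: which classes does each statement name?**

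| Statement | Device | Therapy | Procedure |
|---|---|---|---|
| Protocol 12.1, collection of events | yes | yes | yes |
| Protocol Table 12-2, classification | yes | yes | yes |
| Protocol 14.7, safety assessment | yes | yes | yes |
| SAP 7.10, opening scope | yes | yes | yes |
| SAP 7.10, MedDRA summary and general tables | counted, no class named | counted, no class named | counted, no class named |
| SAP 7.10, relatedness categorisation | yes | yes | **no** |
| SAP 7.10, related-event summary | yes | yes | **no** (deaths from any cause are included) |
| SAP 7.10, serious-event narratives | yes | yes | **no** |

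No visible redaction in SAP 7.10 explains the last three rows.

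**Step 2: what happens to an event under the SAP as written?**

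- Serious, non-fatal, procedure-related only: counted in the general and MedDRA tables and in the serious-event count. It has no relatedness category, is not in the related-event summary and has no narrative.
- Serious, and related to procedure and also to device or therapy: in the related-event summary and narrated, but the link to the procedure is not shown.
- Fatal: covered by the summary of deaths whatever its cause. A narrative is planned only if the event is device- or therapy-related.
- Non-serious, procedure-related only: counted in the general tables, with no relatedness category and not in the related-event summary.

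**Step 3: can the missing class be recovered from the planned tables?** Only in part. Protocol 10.18 and 12.1 limit collection to the three related types, so the overall event count less the device- or therapy-related event count should come close to the count related to procedure alone. Three limits remain:

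- Events related to both device and procedure stay inside the device count.
- Counts of subjects do not subtract, because one subject may have events of both kinds.
- Protocol 12.1 grades causality on five levels, of which only the upper three count as related. Any recorded event graded below that for every class would fall into the remainder.

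**The case against.** The strongest reply is that little is lost. The general and MedDRA tables are not restricted by relatedness, so procedure-related events, including serious ones, are counted and coded. Because the protocol sets out to collect only device-, therapy- and procedure-related events, the overall table is in substance a table of all related events. The protocol still requires the procedure classification, so the gap lies in SAP reporting and not in data capture. The device-related definition in Table 12-1 is broad and takes in introduction tools, so some surgical complications would also be judged device-related and be narrated. Protocol 14.7 asks for frequency tables and a summary by seriousness. It requires neither a relatedness breakdown nor narratives, so the SAP does not breach it on those outputs.

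Most of this stands. A reader might infer from the three sentences that procedure-related events drop out of the safety report, or that the overall burden of related events would be understated. The documents do not support either reading, because the unrestricted tables carry the total. Nor can the gap be sized by counting classes or procedures: neither measures affected events, and no event rate is given.

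What the reply does not answer is the mismatch inside SAP 7.10. The section commits to characterising procedure-related events and then plans no output that identifies them. Having chosen to break events down by relatedness and to write narratives, the SAP gives no reason for leaving out one of the classes it has just named.

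**Conclusion.** The point holds as an internal inconsistency in the SAP's safety reporting. Procedure is missing from the relatedness categorisation, the related-event summary and the serious-event narratives, although SAP 7.10 and protocol 14.7 both name it. The main practical effect falls on serious, non-fatal events judged procedure-related and neither device- nor therapy-related: they would have no narrative and would be absent from the related-event summary. The number of such events cannot be stated from the documents. The total of adverse events, the count of serious events and the summary of deaths are unaffected, as are the primary and secondary analyses.

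This rests on two assumptions: that the three sentences will be applied as written, and that no procedure-related output is specified in text not visible here.

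**What to change.** In SAP 7.10, add procedure to the three sentences:

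- categorise events by relationship to *device, therapy and/or procedure*;
- summarise *all device-, therapy- or procedure-related adverse events*, keeping the summary of deaths;
- provide a narrative for *each serious device-, therapy- or procedure-related adverse event*.

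The cost is a wording change, one extra category in the relatedness tables and possibly a few more narratives. Table 12-2 already requires the classification, so no new judgement is asked of sites. The case report form is not among the documents, so the sponsor should confirm that procedure relatedness is held as a separate field.

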## 7.5 Product Use

The Medtronic Intellis™ with AdaptiveStim™ Technology Neurostimulation System and related components and accessories are commercially available for SCS in the United States and shall be used in accordance with commercial labeling. Exposure to the study product is considered from the time the subject is first exposed to the neurostimulation system, at the beginning of the device trial, until the product is explanted, or the subject discontinues from the study, if later.

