### **10.12.4 12-Month/Final Study Visit**

The 12-Month/Final Study visit will occur 360 days  $\pm$  30 days after device activation (Day 0). At the completion of this visit subjects will be programmed per standard of care and exited from the study. Imaging may be performed to assess for lead migration if deemed necessary by the investigator.

The following information will be collected during the 12-Month Follow-up visit:

- VAS
- [REDACTED]
- [REDACTED]
- [REDACTED]
- [REDACTED]

- Programming parameters/device interrogation report(s) with initial and final settings
- Imaging (if performed)
- Changes to pain medications
- AEs/DDs

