### **10.16 System Modification**

A system modification will be reported in the event the initially implanted device requires invasive modification. System modifications (e.g. lead or device revision, replacement, or explant) may occur due to ineffective or loss of therapy, adverse event, or device deficiency. In the event of a system modification, the follow-up schedule for the subject will remain unchanged. If a system modification occurs, contact a member of the Medtronic study team as the decision to allow the subject to continue with the study will be handled on a case-by-case basis.

The following information will be collected for a system modification:

- Device interrogation report(s) with initial and final programmed settings from the old and new implantable neurostimulator (INS) uploaded via CDU, if replaced and subject remains in the study
- If any portion of the implanted system is replaced, record all changes in source documentation and device identification CRF (e.g. new lead model/serial number)
- AEs/DDs

All explanted product should be returned to Medtronic for analysis when permissible by local laws and regulations. See [Section 7.7](#) for product return details.

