## **10.21 Subject Exit, Withdrawal or Discontinuation**

A subject has the right to withdraw from the study at any time and for any reason without prejudice to his/her future medical care by the principal investigator or institution. Subjects will be provided standard medical care by their physician after their study participation ends.

If a subject is withdrawn from the study, the reason for withdrawal shall be recorded on a study exit eCRF and in the subject's medical record. Subjects are urged to remain in the study as long as possible but may be exited from the study for any of the following situations:

- Eligibility criteria not met
- Pregnancy
- Failure to follow study requirements
- Subject death
- Subject lost to follow-up (LT FU)
- Subject chooses to withdraw (e.g., consent withdrawal, relocation to another geographic location)
- Investigator deems withdrawal necessary (e.g., medically justified, inclusion/exclusion criteria not met, failure of subject to maintain adequate study compliance)
- Adverse events
- Normal study completion

A study exit eCRF, including reason for exit, is required for all subjects and will be completed for any enrolled subject who permanently discontinues from the study or completes the protocol-required study follow-up and has completed the study. Prior to exiting a subject from the study, it is recommended to follow the subject until all ongoing device, therapy, and/or procedure related AEs are resolved or unresolved with no further actions planned. Following exit, subjects will continue to receive standard medical care. Upon exiting from the study, no further study data will be collected, or study visits will occur for the subject. All data available through the time of the subject's exit will be used for analysis. If discontinuation is because of safety or lack of effectiveness, the subject may be asked to be followed for collecting safety data outside the clinical investigation.

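### Device exposure ends at the later of explant and study exit, so a subject explanted without replacement who stays in follow-up accrues exposure with no device present

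*SAP*

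**What the plan says.** SAP 7.10 promises a summary of device exposure in months, by analysis set, with mean, standard deviation, minimum and maximum. Exposure starts at the beginning of the device trial and continues "until the product is explanted, or the subject discontinues from or completes the study, if later". Protocol 7.5 has the same rule without completion: "until the product is explanted, or the subject discontinues from the study, if later".

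SAP 7.10 then derives DTM-LE exposure by the same method for subjects programmed within DTM-LE limits, cutting it off at the date of reprogramming outside them.

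Protocol 10.16 foresees explant during follow-up: "System modifications (e.g. lead or device revision, replacement, or explant) may occur due to ineffective or loss of therapy, adverse event, or device deficiency". It goes on: "In the event of a system modification, the follow-up schedule for the subject will remain unchanged". Whether the subject stays is left open: "the decision to allow the subject to continue with the study will be handled on a case-by-case basis".

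At the end of follow-up, Protocol 10.12.4 says: "At the completion of this visit subjects will be programmed per standard of care and exited from the study". A completer thus normally leaves with the system in place.

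**The concern.** Exposure should measure how long a subject had the device. With *if later*, the exit date replaces the explant date whenever exit comes after explant. For a subject explanted and kept in follow-up, the quantity becomes length of follow-up, not time on the device.

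At stake is the accuracy of a pre-specified summary. The error falls on a particular kind of subject, because the reasons for modification in Protocol 10.16 are lost or ineffective therapy, an adverse event or a device deficiency. It can also hide the shortest exposure among implanted subjects, since one early explant could define the minimum. It carries into DTM-LE exposure as well: an explanted subject never reprogrammed out of limits has no cut-off event before study exit.

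**Working it through.** The documents state no exposure figure to reproduce, so the check compares the rule as written with the alternative on the study's own timeline.

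**Inputs from the documents**
- Protocol Table 10-2: device trial up to 7 days, implant up to 35 days after trial end, activation (Day 0) 9 to 16 days after implant, final visit at Day 360.
- Sample size section of both documents: up to 56 enrolled, 40% attrition before implant.

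**Assumptions**
- Day of explant and number of explanted subjects who stay to the 12-Month visit. Neither is given.
- 30.4375 days per month. The SAP gives no conversion.

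**Rules compared**
- As written: end = max(explant date, exit date).
- Alternative: end = min(explant date, exit date).
- Excess = exit date − explant date, if exit is later; otherwise 0.

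**Timeline.** With the longest pre-activation windows, trial start to Day 0 is 7 + 35 + 16 = 58 days. Trial start to the Day 360 visit is 58 + 360 = 418 days, or 418 / 30.4375 = 13.7 months.

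**Number implanted.** 56 × 0.60 = 33.6, about 34.

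**One subject explanted without replacement and followed to Day 360**

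| Explant (assumed) | Earlier-of rule | As written | Excess | Added to mean (excess / 34) |
|---|---|---|---|---|
| Day 30 | 88 d (2.9 mo) | 418 d (13.7 mo) | 330 d (10.8 mo) | 0.32 mo |
| Day 90 | 148 d (4.9 mo) | 418 d (13.7 mo) | 270 d (8.9 mo) | 0.26 mo |
| Day 180 | 238 d (7.8 mo) | 418 d (13.7 mo) | 180 d (5.9 mo) | 0.17 mo |
| Day 270 | 328 d (10.8 mo) | 418 d (13.7 mo) | 90 d (3.0 mo) | 0.09 mo |

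The 58 days before activation cancel in the excess.

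**In whole months from activation.** Explant at month 4 with follow-up to month 12 gives 12 − 4 = 8 months of excess, and 8 / 34 = 0.24 month on the mean. That is 0.24 / 13.7, about 2% of the scheduled span. Three such subjects would add 24 / 34 = 0.71 month.

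**Minimum.** In the Day 90 row the subject's true exposure is 4.9 months, but the recorded value is 13.7. If that subject had the shortest exposure in the set, the reported minimum is wrong.

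**Exit at explant.** The two dates coincide, both rules agree and the excess is 0.

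**The case against.** The strongest case for leaving the text alone has four parts.

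- **Few subjects are affected.** Staying in the study after a modification is decided individually, and the only specific provision for it in Protocol 10.16 concerns a replaced neurostimulator, where a device is still present. This stands as a limit on size. It does not remove the problem, because explant is named there and continuation after it is not ruled out.
- **The wording may have a purpose.** It may be meant to stop trial-lead removal from ending exposure, or to cover safety follow-up after explant. Neither document says so. SAP 7.10 already sets the safety window separately, from the Device Trial Start Visit to study exit. The trial-lead point can be stated directly.
- **Subjects who exit with the device in place are handled well enough.** A reader might infer that the rule fails for most implanted subjects, because the later date would be a future explant and Protocol 10.21 says "Upon exiting from the study, no further study data will be collected, or study visits will occur for the subject". The documents do not support that reading. Discontinuation and completion are named as end events in the SAP, explants during the study are reported, and Protocol 10.21 bases analysis on data up to exit. With no recorded explant, exit is the workable end date. What remains is an unstated default that merits a clause.
- **Trial failures hardly matter.** They are exited, and following them until related events settle is only recommended. The synopsis definitions of the implanted, completers and per-protocol sets all require implant. The detailed definitions in SAP 7.1.3 cannot be seen, so no effect of these subjects on a table can be shown. They still need an end date if exposure is summarised for all enrolled subjects.

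**Conclusion.** The rule as written gives a wrong value in a situation the protocol itself provides for: explant without replacement followed by continued follow-up. The error for such a subject is the whole interval from explant to exit, 3.0 to 10.8 months for explant between Day 270 and Day 30. Each adds about 0.1 to 0.3 month to the mean over about 34 implanted subjects. These figures rest on assumed explant times, on the subject staying to the 12-Month visit, and on the planned 40% attrition before implant.

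A reader might also infer that longer exposure makes the safety results look more favourable. The planned tables do not bear this out. Adverse events and device deficiencies are reported as counts and percentages of subjects, with no rate per month of exposure, so no planned safety figure changes. The primary endpoint, the change in overall pain VAS, does not use exposure either. The effect is confined to the descriptive exposure summary, including its DTM-LE part. It is small, but worth correcting before the analysis.

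**What to change.** In SAP 7.10 and Protocol 7.5, replace the *if later* rule with these statements:

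1. Exposure ends at the earlier of (a) explant of the implanted system without replacement and (b) study discontinuation or completion.
2. If no explant is recorded, the exit date is used.
3. Removal of trial leads before permanent implant does not end exposure for subjects who are then implanted.
4. For subjects never implanted, exposure ends at trial-lead removal where that date is recorded; otherwise at the Device Trial End Visit or study exit, whichever is earlier.

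DTM-LE exposure then inherits the corrected end date, in addition to its existing reprogramming cut-off.

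**Cost.** A short paragraph in each document and a changed date derivation. The change to Protocol 7.5 is an amendment and follows the approval route in Protocol 16.6. The fallback in statement 4 is needed because neither Protocol Table 10-1 nor the Device Trial End data list names a lead-removal date, and the case report forms are not available to check. The downside is that reported exposure becomes slightly shorter.
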